8.0 TREATMENT MANAGEMENT

8.1 General instructions

- The NCI CTCAE v4.0 must be used to grade the severity of AEs.
- All treatment decision must be based on the AE requiring the greatest modification.
- Drug doses that have been reduced may not be re-escalated.
- All hematologic, gastrointestinal, and genitourinary toxicities must be < Grade 2 prior to initiating Dose 1 of study therapy. Patients unable to receive Dose 1 will be considered screen failures.

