8.3 Dose modifications for durvalumab and tremelimumab

The instructions for management of toxicities during durvalumab and tremelimumab are outlined in [Table 7](#). Dosing of study therapy will be done in tandem:

- When study therapy doses are to be maintained, **both** durvalumab and tremelimumab doses will be maintained on the same dose level.

- When a dose reduction is indicated, **both** durvalumab and tremelimumab will be reduced to the same dose level (e.g., Dose level 1).
- When discontinuation of study therapy is indicated, durvalumab and tremelimumab will be discontinued at the same time.

Table 5. Dose levels for durvalumab

Durvalumab	Dose Level 0 Starting Dose	Dose Level –1	Dose Level –2
		1500 mg	750 mg

Table 6. Dose levels for tremelimumab

Tremelimumab	Dose Level 0 Starting Dose	Dose Level –1	Dose Level –2
		75 mg	40 mg

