8.4 Dose modification and management of toxicities

All toxicities will be graded according to CTCAE version 4.0. Following the first dose of durvalumab and tremelimumab, subsequent administration of durvalumab and tremelimumab can be modified based on toxicities observed as described in [Sections 8.5, 8.6, and 8.7](#). For adverse events (AEs) that are considered at least partly due to administration of durvalumab or tremelimumab, the following general guidance may be applied:

- Treat each of the toxicities with maximum supportive care (including holding the study therapy suspected of causing the toxicity where required).
- All dose modifications should be documented with clear reasoning and documentation of the approach taken.
- In addition to the criteria for permanent discontinuation of study therapy based on toxicity grade, permanently discontinue study therapy for the conditions outlined in [Section 8.2.2](#).

Table 7. Treatment management for study therapy (durvalumab and tremelimumab)

CTCAE v4.0 Adverse Event	CTCAE v4.0 Grade	Action to be Taken with Study Therapy	
		Tremelimumab	Durvalumab
Cardiac Disorders			
Myocarditis (See Sections 8.5.1 and 8.5.12)	1	For suspected myocarditis: Hold study therapy until full diagnostic work up. Initiate steroid therapy and appropriate management. If study therapy is held, resume after complete resolution to Grade 0 after completion of the steroid taper, resume at the next scheduled dose.	
	2	Hold study therapy dose until resolution to Grade 0. If toxicity rapidly improves to Grade 0, then: The decision to reinstitute study therapy will be based upon treating physician’s clinical judgment and after completion of steroid taper. If toxicity does not rapidly improve, permanently: Discontinue study therapy.	
	3-4	Discontinue study therapy	
Endocrine disorders			
Endocrinopathy (e.g., hyperthyroidism, hypothyroidism, Type 1 diabetes mellitus, hypophysitis, hypopituitarism, and adrenal insufficiency; exocrine event of amylase/lipase increased also included in this section) (See Sections 8.5.1 and 8.5.8).	1	No dose modifications.	

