Platelet count decreased (See Section 8.5.11.)	2	Hold until \leq Grade 1 or baseline, then resume and: Maintain dose or \downarrow one dose level.	Hold until \leq Grade 1 or baseline, then resume and: Maintain dose
	3	Hold until \leq Grade 1 or baseline, then resume and: \downarrow one dose level.	Hold until \leq Grade 1 or baseline, then resume and: Maintain dose
	4	Discontinue study therapy	
	Musculoskeletal and connective tissue disorders		
Myositis/Polymyositis (See section 8.5.13)	1	No dose modifications.	
	2	Hold study therapy dose until resolution to Grade ≤ 1 . Discontinue study therapy if it does not resolve to Grade ≤ 1 within 28 days or if there are signs of respiratory insufficiency.	
	3	Hold study therapy dose until resolution to Grade ≤ 1 . Discontinue study therapy if Grade 3 imAE does not resolve to Grade ≤ 1 within 28 days or if there are signs of respiratory insufficiency.	
	4	Discontinue study therapy	

Table 7 continued on next page.

Table 7. Treatment management for study therapy (continued)

CTCAE v4.0 Adverse Event	CTCAE v4.0 Grade	Action to be Taken with Study Therapy	
		Tremelimumab	Durvalumab
Nervous system disorders			
Neurotoxicity (to include but not be limited to limbic encephalitis and autonomic neuropathy, excluding Myasthenia Gravis and Guillain-Barre) (See Sections 8.5.1 and 8.5.9.)	1	Hold study therapy during neurotoxicity work-up. If diagnosis of Myasthenia Gravis or Guillain-Barre is confirmed, discontinue study therapy. Otherwise, maintain study dose level.	
	2,3	Hold study therapy during neurotoxicity work-up. Once elevations have resolved to \leq Grade 1, and if 
 no systemic steroid therapy has been initiated, then resume: \downarrow 1 dose level. systemic steroid therapy has been initiated –after completion of the steroid taper: resume \downarrow 1 dose level or discontinue If steroid taper completion is $>$ 28 days: discontinue further study therapy. 	
	4	Discontinue study therapy	
Peripheral neuromotor syndrome (such as Guillain-Barre and myasthenia gravis) (See Sections 8.5.1 and 8.5.10.)	1	No dose modifications.	
	2	Hold study therapy dose until resolution to Grade \leq 1. Permanently discontinue study therapy if it does not resolve to Grade \leq 1 within 28 days or if there are signs of respiratory insufficiency or autonomic instability.	

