8.5 Immune-mediated adverse events (imAEs)

Immune-mediated adverse events/imAEs are important risks of interest and include: pneumonitis/ interstitial lung disease (ILD), diarrhea/colitis, hepatitis and increases in transaminases, nephritis and increases in serum creatinine, dermatitis/rash and pruritus, endocrinopathy (hypo- and hyperthyroidism, adrenal insufficiency, hypophysitis/hypopituitarism and Type I diabetes mellitus), myocarditis, neuropathy/neuromuscular toxicity (such as myasthenia gravis and Guillain-Barre) and pancreatitis. In addition, infusion-related reactions and hypersensitivity/anaphylactic reactions with a different underlying pharmacologic etiology are also considered AESIs. See [Section 10.2](#).

Other inflammatory responses that are rare with a potential immune related etiology are also considered as AESIs and include but are not limited to pericarditis, sarcoidosis, uveitis, and other events involving the eye, skin, hematological and rheumatological events. It is possible that events with an inflammatory or immune mediated mechanism could occur in nearly all organs ([Durvalumab IB 2018](#)).

Thorough evaluation of these events should be performed to rule out any alternative etiology (e.g., disease progression, concomitant medications, or infections). In the absence of a clear alternative etiology, all events should be considered potentially immune related. For study treatment dose management related to imAEs, see [Table 7](#).

The following guidelines are *recommended* as management of the following immune-mediated reactions.

8.5.1 **Overall management for imAEs**

- Patients should be thoroughly evaluated to rule out any alternative etiology (e.g., disease progression, concomitant medications, infections, etc.).
- In the absence of a clear alternative etiology, all events should be considered potentially immune related.
- Symptomatic and topical therapy should be considered for low-grade (Grade 1 or 2, unless otherwise specified) events.
- For persistent (greater than 3 to 5 days) low-grade (Grade 2) or severe (Grade ≥ 3) events promptly start prednisone 1-2mg/kg/day PO or IV equivalent unless otherwise noted in subsequent sections.

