Patients should be evaluated to rule out any alternative etiology (e.g., disease progression, infections, metabolic syndromes and medications, etc.). It should be noted that the diagnosis of immune-mediated peripheral neuromotor syndromes can be particularly challenging in patients with underlying cancer, due to the multiple potential confounding effects of cancer (and its treatments) throughout the neuraxis. Given the importance of prompt and accurate diagnosis, it is essential to have a low threshold to obtain a neurological consult. **If Myasthenia Gravis or Guillain-Barre is confirmed, discontinue study therapy.**

Neurophysiologic diagnostic testing (e.g., electromyogram and nerve conduction investigations, and “repetitive stimulation” if myasthenia is suspected) are routinely indicated upon suspicion of such conditions and may be best facilitated by means of a neurology consultation.

It is important to consider that the use of steroids as the primary treatment of Guillain-Barre is not typically considered effective. Patients requiring treatment should be started with IV IG and followed by plasmapheresis if not responsive to IV IG. See [Table 7](#).

- *Grade 1:*
 - Hold study therapy.
 - Contact DSSM.
 - Care should be taken to monitor patients for sentinel symptoms of a potential decompensation as described above.
 - Obtain a Neurology consult unless the symptoms are very minor and stable. If Myasthenia Gravis or Guillain-Barre is confirmed, discontinue study therapy and report event to DSSM.
- *Grades 2, 3 and 4:*
 - Hold study therapy during work-up of symptoms. If Myasthenia Gravis or Guillain-Barre is confirmed, discontinue study therapy. If negative hold therapy until \leq Grade 1 and prednisone dose is \leq 10 mg/day or the equivalent.
 - Report event to DSSM.
 - Care should be taken to monitor patients for sentinel symptoms of a potential decompensation as described above.
 - Obtain a Neurology consult.
 - Sensory neuropathy/neuropathic pain may be managed by appropriate medications (e.g., gabapentin, duloxetine, etc.).

MYASTHENIA GRAVIS

- Steroids may be successfully used to treat Myasthenia Gravis. Important to

consider that steroid therapy (especially with high doses) may result in transient worsening of myasthenia and should typically be administered in a monitored setting under supervision of a consulting neurologist.

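### Table 7 and Section 8.5.10 give opposite dosing instructions for an unconfirmed Grade 1 peripheral neuromotor syndrome, and no express precedence is stated

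*Combined protocol and SAP*

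**What the plan says.** **Table 7 (protocol Section 8.4, nervous system disorders).** The row is headed "Peripheral neuromotor syndrome (such as Guillain-Barre and myasthenia gravis"). Its Grade 1 action is "No dose modifications". At Grades 2 and 3 the same row holds treatment until the event falls to Grade 1 or lower, and at Grade 4 it discontinues.

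**Section 8.5.10.** For the same syndromes at Grade 1, the first instruction is "Hold study therapy". The site is then to contact DSSM, watch for warning signs, and obtain a Neurology consult, which may be skipped if symptoms are slight and not changing. If either named disease is confirmed, treatment stops.

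**Pointers between the sections.**
- Section 8.3: "The instructions for management of toxicities during durvalumab and tremelimumab are outlined in" Table 7.
- Section 8.5: "For study treatment dose management related to imAEs, see" Table 7. It introduces its own organ-specific advice as recommended.
- Section 8.4: "subsequent administration of durvalumab and tremelimumab can be modified based on toxicities observed as described in" Sections 8.5, 8.6 and 8.7.
- The Table 7 row cites 8.5.10, and 8.5.10 cites Table 7.

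**Section 8.2.2.** A diagnosis of Guillain-Barre or myasthenia gravis requires discontinuation, with no grade threshold.

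**The concern.** An investigator with a patient who has new, mild neuromotor symptoms and a dose due will find two answers in the protocol. One gives the dose and the other withholds it. The investigator cannot comply with both, and two sites could treat the same presentation differently while each follows a written instruction.

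What is at stake is patient safety. The introduction to 8.5.10 says that some of these patients deteriorate without warning, with death as the worst outcome. It adds that diagnosis is difficult in people with cancer. The conflict therefore falls on the patient who has symptoms but no diagnosis yet. The discontinuation rule in 8.2.2 is triggered by a diagnosis, so it does not settle what to do before one is made.

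**Working it through.** The plan has no figure to reproduce on this point. The check is a comparison of texts, with a short calculation on scheduling at the end.

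**1. Do the two texts cover the same case?** Yes. Both name Guillain-Barre and myasthenia gravis as examples, both address Grade 1, and each cites the other.

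**2. Could the Table 7 wording be read as allowing a hold?** Not reasonably. In the same row and column, Grades 2 and 3 state the hold explicitly. A cell that meant a hold would say so.

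**3. Does another rule settle it?**
- 8.3 and 8.5 favour Table 7. With the recommended status of the 8.5 guidance, they give a reader a basis for following the table.
- 8.4 favours 8.5, in permissive terms.
- The row and 8.5.10 refer to each other, so following the references leads back to the start.
- Section 8.1 says "All treatment decision must be based on the AE requiring the greatest modification". This ranks adverse events against one another. It does not rank two texts about the same event.

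The balance of pointers leans towards Table 7, but none of them says what happens if the texts differ.

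**4. Which patients are affected?** Those at Grade 1 without a confirmed diagnosis of either disease. Confirmed cases stop under 8.2.2 and 8.5.10.

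**5. Which way does the rest of the protocol lean?** The neighbouring neurotoxicity row in Table 7 says at Grade 1: "Hold study therapy during neurotoxicity work-up. If diagnosis of Myasthenia Gravis or Guillain-Barre is confirmed, discontinue study therapy". Otherwise it keeps the dose level. So the row that names the two diseases is less cautious at Grade 1 than the row whose heading excludes them. Section 8.5.10 also lets a Grade 2 to 4 patient with a negative work-up restart at Grade 1 or lower, provided the steroid dose is low. Resuming at Grade 1 after a negative evaluation is therefore consistent with the protocol's own approach.

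**6. Is the 8.5.10 hold complete as written?** No. Its Grade 1 bullets give no condition for restarting. Under 8.2.2, a continuous hold of more than 28 days for toxicity forces discontinuation.

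**7. Could a hold move the scans?** Only if it shifts the cycle schedule, which the documents do not establish for this hold. Section 8.2.1 restarts steroid-related holds on Day 1 of the next scheduled cycle, and 8.2 provides for missed doses to be recorded. If a hold of h days did shift the 28-day cycles, the scan after Cycle c would fall at week (28c + h)/7:
- No hold: (56 + 0)/7 = 8 after Cycle 2; (112 + 0)/7 = 16 after Cycle 4.
- h = 14: 70/7 = 10 and 126/7 = 18.
- h = 28, the longest hold before forced discontinuation: 84/7 = 12 and 140/7 = 20.

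A delay of up to 3 days is within the dosing window in 8.2.

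**The case against.** The strongest reply is that the protocol does guide the reader. Sections 8.3 and 8.5 send dosing to Table 7, Sections 7.1 and 8.2.2 also refer there, and the 8.5 guidance is only recommended. The counter-pointer in 8.4 is permissive. This largely stands. A reader might infer that nothing indicates which text to use, and that would go too far. But these are pointers and not a precedence clause, and following them gives the dose in the case where 8.5.10 says to withhold it. One of the two texts still has to change.

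A second reply joins the neurotoxicity row to Section 8.1. An undiagnosed patient might fit both rows, because the neurotoxicity row's Grade 1 text anticipates a later diagnosis of either disease. The greatest-modification rule would then select the hold. This is a fair reading but not a secure one, because that row's heading excludes both diseases. A dosing decision should not depend on such a chain of inference.

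Third, safeguards exist: the DSSM contact at Grade 1, the weekly call in Section 14.3 that investigators with a patient on therapy must join, and the rule in 8.2.2 that treatment stops when the investigator or sponsor judges an event to rule out further dosing. These reduce the risk. None of them says which instruction applies.

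Finally, either text could be the one to correct, and choosing the hold is a clinical judgement. That is true. The choice here follows the protocol's own 8.5.10 and its neighbouring row.

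**Conclusion.** The conflict holds. It is one table cell against one bullet, for Grade 1 events not confirmed as Guillain-Barre or myasthenia gravis. It is a wording inconsistency with a possible safety consequence, and it should be corrected.

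Its size cannot be expressed as a rate, because the documents give no incidence for these events. Counting scheduled doses would not help, since that does not measure how often the conflict arises.

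Three stronger readings are not supported:
- **That confirmed disease could go on being dosed.** Discontinuation is already required.
- **That this is the only mismatch of its kind.** For Grade 1 pneumonitis, Table 7 keeps the schedule, under a line that holds until evaluation, while 8.5.3 says to consider holding. For suspected Grade 1 myocarditis, Table 7 holds, while the Grade 1 bullets in 8.5.12 state no hold.
- **That the statistical design is compromised.** The response-rate hypotheses, the 12 and 21 patient stages and the endpoint definitions do not depend on this cell.

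The conclusion assumes that the two quoted instructions are current protocol text and that Grade 1 has the same meaning in both places.

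**What to change.** **Table 7, peripheral neuromotor syndrome, Grade 1 cell.** Replace the present entry with: hold study therapy during evaluation; discontinue if Guillain-Barre or myasthenia gravis is confirmed; otherwise resume and maintain the dose level.

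**Section 8.5.10, Grade 1 hold bullet.** Add the same resumption wording. State also that, where the Neurology consult is waived because symptoms are slight and steady, the hold ends once the investigator's evaluation is complete and DSSM has been contacted. Without this, a patient who needs no consult has no defined end to the hold.

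Grades 2 to 4 need no change for this point.

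**Cost.** The edit is one cell and one bullet. In practice some Grade 1 patients may have a short dose delay. If a hold on the Cycle 2 dose did shift the schedule, the first restaging scan, and so the date on which the patient becomes evaluable under Section 14.2, would move later. The scan after Cycle 4 could then fall beyond the 16-week clinical benefit time point. Stating whether a held dose is skipped or the cycle is moved would remove that uncertainty.

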8.2 Treatment management for durvalumab and tremelimumab

The study treatment schedule should be maintained. If necessary, the timing of a treatment may be adjusted to 3 days earlier or 3 days later than the scheduled date of treatment. All doses administered or missed must be recorded.

8.2.1 *Treatment decisions when therapy must be held*

- In the event systemic steroid therapy is initiated for toxicity management, study therapy must be held. The steroid taper should be completed within 28 days. Study therapy may then be resumed after completion of the steroid taper on Day 1 of the next scheduled cycle.
- Note: Should the steroid taper require a slower rate for completion (i.e., > 28 days), further study therapy doses must be discontinued.
- See [Table 7](#) for treatment management.

8.2.2 *Treatment decisions when therapy must be discontinued*

Treatment must be discontinued if:

- If either durvalumab or tremelimumab must be held for > 28 days of continuous delay for other than steroid taper (e.g., toxicity).
- Consent is withdrawn or patient is lost to follow-up. If consent is withdrawn, the patient will not receive any further investigational product or further study observation.
- An adverse event occurs that, in the opinion of the investigator or sponsor, contradicts further dosing.
- The patient becomes pregnant or intends to conceive a child while actively on study.
- Grade 3 or greater infusion reaction occurs.
- Bullous rash.
- Diagnosis of Guillain-Barre and/or Myasthenia Gravis.
- Initiation of alternate cancer therapy including another investigational agent.
- If tumor progression occurs during study therapy, durvalumab must be discontinued. See [Section 11.0](#).

See [Table 7](#) for additional treatment management requirements. Patients who prematurely discontinue study therapy should complete assessments on [Table 2](#).

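### For a Grade 1 peripheral neuromotor syndrome with the diagnosis pending, Table 7 continues dosing while Section 8.5.10, which that row cites, holds it, and no other rule clearly settles which applies

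*Combined protocol and SAP*

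**What the plan says.** Table 7 (protocol Section 8.4) has a row labelled "Peripheral neuromotor syndrome (such as Guillain-Barre and myasthenia gravis", which refers the reader to Sections 8.5.1 and 8.5.10. Its actions by grade are:

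- Grade 1: "No dose modifications".
- Grades 2 and 3: hold until the event is Grade 1 or lower, and stop permanently if it does not resolve "within 28 days or if there are signs of respiratory insufficiency or autonomic instability".
- Grade 4: discontinue.

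Section 8.5.10 covers the same syndromes. Its first instruction at Grade 1 is "Hold study therapy". Its general text adds "If Myasthenia Gravis or Guillain-Barre is confirmed, discontinue study therapy", with no grade limit. Section 8.2.2 lists "Diagnosis of Guillain-Barre and/or Myasthenia Gravis" among the conditions that require treatment to stop, also without a grade limit.

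The neurotoxicity row directly above in Table 7 is labelled as "excluding Myasthenia Gravis and Guillain-Barre". Even so, its Grade 1 cell holds therapy during work-up and then says "If diagnosis of Myasthenia Gravis or Guillain-Barre is confirmed, discontinue study therapy".

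**The concern.** A patient with mild weakness or tingling may be Grade 1 with no diagnosis yet when the next Day 1 arrives. A site working from the table would infuse, and a site working from Section 8.5.10 would not. Each could point to written text.

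Section 8.5.10 itself warns that these patients can decompensate suddenly and that the worst outcome is death. What is at stake is therefore a further dose of the suspected cause before the diagnosis is known. The protocol's hold and discontinue safeguard appears in the table row whose label excludes these two diseases, and is missing from the row that names them.

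**Working it through.** No arithmetic applies; the check is a comparison of the instructions.

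| Source | Grade 1, diagnosis pending | Diagnosis confirmed |
|---|---|---|
| Table 7, neuromotor row | "No dose modifications" | Silent on confirmation |
| Section 8.5.10 | "Hold study therapy" | "If Myasthenia Gravis or Guillain-Barre is confirmed, discontinue study therapy" |
| Section 8.2.2, Guillain-Barre/myasthenia item | Not triggered | Must stop |
| Table 7, neurotoxicity row | Hold during work-up | "If diagnosis of Myasthenia Gravis or Guillain-Barre is confirmed, discontinue study therapy" |

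**Step 1: is the Grade 1 conflict direct?** Yes. The table cell and Section 8.5.10 address the same syndrome at the same grade and give opposite actions.

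**Step 2: does another rule settle it while the diagnosis is open?**

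- Section 8.2.1 forces a hold only once systemic steroids are started, and Section 8.5.10 prescribes none at Grade 1.
- The Section 8.2.2 item acts only on a diagnosis.
- Section 8.1 says to act on the adverse event that calls for the largest modification. That ranks different events; it does not choose between two instructions for one event.
- The cross-references do not fix an order. Section 8.3 places the toxicity instructions in Table 7. Section 8.5 calls its own guidance recommended and sends dose management to Table 7. But Section 8.4 also says doses can be modified as Sections 8.5 to 8.7 describe. The table row cites Section 8.5.10, and the general text of Section 8.5.10 ends by citing Table 7.

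No rule clearly settles it.

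**Step 3: what about a confirmed diagnosis?** Just before Table 7, Section 8.4 states that the Section 8.2.2 conditions apply on top of the grade-based criteria. Confirmed Guillain-Barre or myasthenia gravis therefore ends study therapy at every grade, whatever the row says.

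**Step 4: what would the Grade 1 cell need to say?** Section 8.5.10 gives a hold at Grade 1 but no condition for releasing it if the work-up is negative. The neurotoxicity row supplies one: keep the dose level. Together the two give a complete instruction in terms the protocol already uses.

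**Step 5: what is exposed?** One infusion day per 28-day cycle: durvalumab 1500 mg, with tremelimumab 75 mg in Cycles 1 to 4 (Table 4). Only an infusion that falls due inside the work-up window is affected.

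**The case against.** The strongest reply is that the protocol, read as a whole, leads to a hold. The row sends the site to Section 8.5.10. Section 8.4 recognises Section 8.5 as a source of dose changes. An undiagnosed patient could also fit the neurotoxicity row, whose Grade 1 cell expects that one of the two diseases may yet be confirmed; if both rows fit, Section 8.1 favours the larger modification. Investigators may also withhold treatment on judgment, and the weekly call in Section 14.3 gives a chance to ask.

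This shows that a careful site would probably hold, and it supports holding as the intended action. It does not remove the conflict: the site must look past the cell that names the syndrome and infer the answer from a row whose label excludes it.

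Three stronger readings are tempting and are not supported:

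- **That the row lets a patient with confirmed disease return at Grades 2 and 3, or continue at Grade 1.** Section 8.4 with Section 8.2.2 forbids this. The row label gives the two diseases as examples, so the hold-and-return route can serve other or unconfirmed syndromes. Section 8.5.10 has its own 28-day route at Grade 3. Nor does the prednisone threshold of 10 mg/day in Section 8.5.10 override Section 8.2.1, which requires the taper to be completed.
- **That expedited reporting misses a Grade 1 case.** Section 10.4.2 sets the threshold for events of special interest at Grade 2, but Section 10.4 opens by covering all events listed in Section 10.2, where neuromuscular toxicity appears without a grade. The text is ambiguous, and the point does not depend on it.
- **That the chance of harm can be quantified.** The documents give no incidence for these syndromes. An assumed incidence would describe any case among the patients, not a Grade 1 case under work-up with an infusion due.

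**Conclusion.** The concern holds for the Grade 1 cell while the diagnosis is pending. There the protocol gives two opposite dosing instructions and no clear order between them. At Grades 2 and 3 the row omits the stop-on-confirmation line, but the requirement is in force through Sections 8.4 and 8.2.2, so that is a matter of clarity only. At Grade 4 there is no conflict.

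Severity is minor. The problem is confined to one cell and to the period before diagnosis, and the objective response rate and the two-stage decision rule do not depend on it. It still merits correction because the harm that Section 8.5.10 describes is serious and the repair is simple. The conclusion rests on the wording alone and needs no assumption about incidence.

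**What to change.** Reword the peripheral neuromotor row of Table 7 at the next amendment.

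- **Grade 1:** replace "No dose modifications" with an instruction to hold study therapy during work-up, followed by "If Myasthenia Gravis or Guillain-Barre is confirmed, discontinue study therapy", and otherwise to keep the current dose level.
- **Grades 2 and 3:** leave the present hold, the 28-day limit and the stop for respiratory or autonomic signs exactly as they are. Add "If Myasthenia Gravis or Guillain-Barre is confirmed, discontinue study therapy" with a reference to Section 8.2.2. State that resumption is possible only when both diseases have been ruled out, and that Section 8.2.1 applies if systemic steroids are given.
- **Grade 4:** no change.

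The existing Grade 2 and 3 text should not be made conditional on a negative work-up. That would remove from the row both the hold during work-up and the respiratory/autonomic stop.

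The cost is the rewording of one table row, with no added visits, tests or patients. A Grade 1 hold may delay a dose, and a continuous hold beyond 28 days would end treatment under Section 8.2.2; Section 8.5.10 as written already carries that consequence.
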